11.3.4 Medical History and Concomitant Diseases

Medical history is defined as any condition that started and ended prior to Screening. Medical history will be coded using Medical Dictionary for Regulatory Activities (MedDRA) version 18.0 and listed separately by sequence, System Organ Class (SOC) and Preferred Term (PT) within SOC.

A concomitant disease is defined as any condition that started after ICF signature or was started prior to the Screening Visit and is still ongoing at the Screening Visit.. Concomitant disease will be coded using MedDRA version 18.0 and listed separately by sequence, SOC and PT within SOC.

Partial dates will not be imputed, but assumptions will be made as follows to assign to either medical history or concomitant diseases:

Date information	Assign as
Missing stop date	Concomitant disease
Partial date, e.g., --May2012, or ----2011. If month/year is the same as, or later than the month and/or year of Screening.	Concomitant disease
Partial date, e.g., --May2012, or ----2011. If month and/or year is earlier than the month and/or year of Screening.	Medical history

The data will be presented in the below outputs:

TFL number	Title
TABLES	
15.2.1.6	Summary of Medical History – Safety Population
15.2.1.7	Summary of Concomitant Diseases – Safety Population
LISTINGS	
15.3.1.8	Listing of Medical History and Concomitant Disease

11.3.5 Other Data

Other data collected at Screening and/or Admission will be listed by sequence and subject. These data are as follows:

- Urine cotinine test
- Urine pregnancy test
- Chest x-ray
- Urine drug screen
- Serology
- Alcohol breath test
- Prior and concomitant medication
- Product Test and Demonstration

The data will be presented in the below outputs:

TFL number	Title
TABLES	
15.2.1.1	Summary of Subject Disposition – Screened Population
LISTINGS	
15.3.1.4	Listing of Product Test, Willingness to interrupt smoking up to 6 days, Willingness to Quit Smoking
15.3.1.5	Listing of Safety Laboratory Entry Criteria
15.3.6.3	Listing of Prior and Concomitant Medication

11.4 Measurements of Product Compliance

Levels of CO in exhaled breath will be measured to evaluate the exposure to CO (see Section 11.6.2.2.1 “Exhaled CO and COHb”), and to monitor compliance during the following study days (see Section 6.3.3 “Compliance to Product Allocation”):

- Admission on Day -3
- Wash-out on Day -2/-1 and Day 2
- Single use Day 1 and Day 3
- Discharge on Day 4

CO data will be listed and summarized by sequence for all study days and timepoints as continuous variable and with the categorization ≤ 10 ppm and >10 ppm.

Values above 10 ppm will be highlighted in listings and be considered as non compliance if such values are observed prior to first product use on the single use days or during the washout days. CO data leading to exclusion of subjects from the analysis will be evaluated during the pre-analysis blind data review.

Number and percentage of subjects considered as non compliant during the study will be tabulated by sequence and study days for the Randomized population

The data will be presented in the below outputs:

TFL number	Title
TABLES	
15.2.4.9.1	Descriptive Statistics of Exhaled CO (ppm) During Single Use Days Continuous Measurements– PK Population
15.2.4.9.1.1	Descriptive Statistics of Exhaled CO (ppm) During Single Use Days by Sex – PK Population
15.2.4.9.1.2	Descriptive Statistics of Exhaled CO (ppm) During Single Use Days by Nicotine Level – PK Population
15.2.4.9.2	Descriptive Statistics of Exhaled CO (ppm) During Single Use Days Categorical Measurements– PK Population
15.2.4.10.1	Descriptive Statistics of Exhaled CO (ppm) During Days -3,-2, -1, 2 and 4 Continuous Measurements– PK Population
15.2.4.10.1.1	Descriptive Statistics of Exhaled CO (ppm) During Days -3,-2, -1, 2 and 4 by Sex – PK Population
15.2.4.10.1.2	Descriptive Statistics of Exhaled CO (ppm) During Days -3,-2, -1, 2 and 4 by Nicotine Level – PK Population
15.2.4.10.2	Descriptive Statistics of Exhaled CO (ppm) During Days -3,-2, -1, 2 and 4 Categorical Measurements– PK Population
15.2.5.1	Descriptive Statistics of Compliance– Randomized Population
LISTINGS	
15.3.3.4	Listing of Exhaled Breath CO (ppm) and Measurement Times

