6 INVESTIGATIONAL PLAN

6.1 Study Design

[figure not shown]
This is a randomized, controlled, 2-period, 2-sequence, single-use crossover study. Each subject will receive CHTP 1.1 M and mCC (Figure 1 Study Flow Chart).

The end of the study is defined as the date when the last subject completes his/her 7-day safety follow-up period.

Subjects that terminate the study after Enrolment and prior to completion of the study will be asked to undertake early termination procedures.

1) Screening and Admission (from the ICF Signature to the Enrolment at Admission):

A Screening Visit will be conducted within 4 weeks (Day -31 to Day -4) prior to Admission to the investigational site (Day -3). A demonstration of the CHTP 1.1 M will be done by the site collaborators during the Screening Visit. Screening procedures do not necessarily have to be conducted on the same day. On Day -3 (Admission), after all inclusion/exclusion criteria are checked, all eligible subjects will be enrolled and perform a product test using 3 to 5 CHTPs 1.1 M. After product test, subjects not ready to use the CHTP 1.1 M will be discontinued. All subjects that are not enrolled are considered as screen failures. Subject will be instructed not to smoke in the morning prior to Admission. After Admission, smoking will not be allowed until blood drawing for the assessment of CYP2A6 activity and spirometry have been performed (Section 9.2). After these assessment procedures, smoking will be allowed until 11.00 PM at Admission.

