**Figure 1 Study Flow Chart****2) The Investigational Period (from Day -2 to Discharge):**

The Investigational period will consist of 2 periods (Period 1, Period 2) with each period consisting of approximately 48 to 57 hours smoking abstinence and 1 day of single product use.

Period 1: From Day -2 to Day 1. After Day 1 product use, the subject will start his/her washout for period 2

Period 2: From Day 2 to Day 3. The products should be used at the same time (within 1 hour) on Day 1 and Day 3

48 eligible, healthy smoking subjects will be randomized to one of 2 sequences:

Table 1 Definition of Randomization Sequences

Sequence	Sample Size
1. CHTP 1.1 M then mCC	24
2. mCC then CHTP 1.1 M	24

Each sex and smoking strata (International Organization for Standardization [ISO] nicotine levels ≤ 0.6 mg vs. >0.6 to 1.0 mg) will have a quota applied to ensure they represent at least 40% of the study population for each Sequence (Sequence 1 and Sequence 2).

Subjects who do not complete the study after randomization will not be replaced.

Subjects will be discharged from the investigational site in the morning of Day 4 after performance of Discharge assessments.

3) The Safety Follow-up Period (from Discharge until Day 11):

A 7-day safety follow-up will be done for the recording of spontaneously reported AEs and SAEs (passive surveillance) and the active follow-up by the investigational site of AEs/SAEs ongoing at Discharge. Any AE will in general be followed-up until resolved, stabilized (*i.e.*, no worsening of the event), or until a plausible explanation for the event has been found.

The end of study for the subject is defined as the date of completion or discontinuation on Subject status form completed. AEs/SAEs not resolved or not stabilized at EOS are to be recorded as ongoing at EOS.

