10.5.1 Major Protocol Deviations

Subjects with major protocol deviations will be identified (at a population level) to determine whether they will be excluded from any of the analysis populations. The following have been identified as the major protocol deviations.

The categories for the major deviations will include, but are not limited to the deviations presented in Table 9.

Table 9: Definition of Major Protocol Deviations

Category	Description
Violation	Violation of inclusion/exclusion criteria
Mis-randomization	Being administered the wrong product according to the randomization schedule
Mis-use of product	Use of any nicotine or tobacco-containing product other than the assigned product during the exposure period, or use of any nicotine tobacco-containing product during wash-out days (e.g. see Section 11.4 "Measurements of Product Compliance").
Concomitant medication	Use of any drugs which are known to affect CYP2A6 activity

Among the above criteria, violations of inclusion criteria 3, 6 to 8, or of the exclusion criteria 1, 3 to 16, and 19 will be assessed for their impact on the PK population and evaluated during the pre-analysis data review meeting (Section 6.3.1 "Methods of Assigning Subjects to Treatment Sequences").

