10.5.2.1 Assessment Windows

On Day 1 and Day 3, subjects will use the product they are randomized to only once in the morning between 6:00 AM and 9:00 AM, and will abstain from the product or other nicotine/tobacco-containing items for the rest of the day. The start of the first product use must be in the window of 6:00 AM to 9:00 AM and should be at the same time (within 1 hour) for both days. The windows reported in Table 11 will be applied to the timing of data collection.

Table 11: Definition of Assessment Windows

Assessment	Nominal Time point(s) (relative to T₀)	Window
Plasma nicotine PK sample (CHTP 1.1 M or mCC)	First sample	Within 15 min prior to T ₀
	2, 4, 6, 8 and 10 min	+ 1 min
	15, 30 and 45 min	+ 2 min
	60 min	+ 3 min
Assessment of cough	2, 4, 6, 9, 12 and 24 h	+ 5 min
	Day -2	06:30AM – 09:00AM
	First assessment	Prior to product use (Day 1 and Day 3)
24 h after T ₀		24 hours (- 30 minutes) after T ₀ of Day 1 and Day3
	First time	Within 15 min prior to T ₀
		15 min, 30 min, 45 min, 1 h and 2 h
4, 6, 9 and 12 h	+10 min	
	COHb blood sampling	First sample
15 min		+ 2 min
60 min		+ 3 min
4 and 12 h		+ 5 min
CO breath test	First measurement	Within 15 min prior to T ₀
	Second measurement	12:00-01:30 PM
	Third measurement	04:00-05:30 PM
	Fourth measurement	08:00-09:30 PM
CYP2A6	COT and HCOT measurements	Prior to smoking

11 PLANNED STATISTICAL METHODS**11.1 General Considerations**

Data analysis will be performed using SAS[®] Version 9.2 or higher.

Data listings will be provided for all data collected, ordered by sequence and subject, unless otherwise stated. Summary statistics and statistical analysis will only be presented for data where detailed in this SAP. All unscheduled assessments will be included in the listings.

Safety data will be summarized for the safety population, PK data will be summarized and analyzed for the PK population, biomarker data will be summarized and analyzed for the PK population unless otherwise stated.

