11.6.2.2 Biomarkers

11.6.2.2.1 Exhaled CO and COHb

COHb measured in blood and exhaled CO will be investigated as a measure of exposure to CO.

CO in exhaled breath will be measured using the Smokerlyzer[®] device such as Micro+[™] Smokerlyzer[®] device or similar. A CO breath test will be conducted once at Day -3 and Day 4. On Day -2, Day -1, Day 1, Day 2, and Day 3, four CO breath tests will be done per day. On Day 1 and Day 3, the first test per day will be performed within 15 minutes prior to T₀ and then between 12:00 PM and 01:30 PM, between 4:00 PM and 05:30 PM, and between 8:00 PM and 09:30 PM. On the wash-out days (Day -2, -1 and Day 2) it will be conducted between 8:00 AM and 09:30 AM, 12:00 PM and 01:30 PM, between 4:00 PM and 05:30 PM, and between 8:00 PM and 09:30 PM.

Tests for COHb measurement will be performed at a local laboratory. Blood samples will be taken as follows at Day 1 and Day 3: a total of five blood samples will be taken. The first sample will be taken within 15 minutes prior to using the first product (T₀). Thereafter the sampling times in relation to T₀ are at 15 minutes, 60 minutes, 4 hours, and 12 hours post-T₀.

Descriptive statistics summarized by product will be produced separately for all scheduled timepoints for exhaled CO and COHb assessments at single use day. This will be done on the PK populations, overall and by the two stratification factors (sex, mCC nicotine level at Admission) as specified in Section 11.1.1 “Stratified Presentation”.

Actual values of blood COHb and levels of exhaled CO will be listed and summarized. The number of subjects with COHb levels $\leq 2\%$ will be summarized for each measurement. The 2% threshold is important because, as reported in (WHO, 2010), COHb elevated above 2% was found to cause ST-segment changes and decreased time to angina.

In addition line graphs will be produced for exposure means (and 95% CI) over all timepoints.

Values of exhaled CO measured during wash-out, admission, and discharge will not be analyzed because they will be collected only for monitoring purposes, however they will be reported as described in Section 11.4 “Measurements of Product Compliance”.

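### The rule that exhaled CO above 10 ppm means non-compliance covers the Day -2 morning test, which can fall only 9 to 10.5 h after permitted smoking

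*SAP*

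**What the plan says.** - **Rule.** SAP Section 11.4: "Values above 10 ppm will be highlighted in listings", and they are "considered as non compliance if such values are observed prior to first product use on the single use days or during the washout days". One such value is enough, and no time point is exempt.
- **Days covered.** The same section lists "Wash-out on Day -2/-1 and Day 2".
- **Last permitted smoking.** Section 6.1: once the CYP2A6 blood draw and spirometry on Day -3 are done, "smoking will be allowed until 11.00 PM at Admission".
- **First wash-out test.** Section 11.6.2.2.1: "On the wash-out days (Day -2, -1 and Day 2) it will be conducted between 8:00 AM and 09:30 AM". The three later tests on those days start at 12:00, 16:00 and 20:00, each with a 90-minute window.
- **Where the label goes.** Section 11.4 tabulates non-compliant subjects by sequence and study day for the Randomized population (Table 15.2.5.1). Table 9 in Section 10.5.1 lists "use of any nicotine tobacco-containing product during wash-out days" as a major deviation and points to Section 11.4 as an example.
- **Safeguard.** Section 11.4 leaves exclusion on CO grounds to a blinded review before analysis. Section 10.3 removes subjects from the PK population only for major deviations that affect whether their data can be evaluated.

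**The concern.** The breath test on wash-out days is meant to detect smoking that the plan forbids. On the morning of Day -2 it also measures what is left of smoking that the plan allowed the evening before, and the rule does not separate the two. A subject who did exactly as told can be labelled non-compliant.

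The blinded review does not correct this, because it is attached to exclusion from the analysis and not to the label. Table 15.2.5.1 would still count the subject under Day -2. Through the cross-reference in Table 9, the subject could also be put forward as a case of wash-out tobacco use. Such errors would not fall at random: they would pick out subjects with the highest CO at the end of Day -3. Nor does the plan ensure a reference value from the end of permitted smoking, since Section 11.6.2.2.1 schedules a single Day -3 breath test and gives no clock time for it.

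**Working it through.** **1. Reproduce the plan's own clock.** The study description gives "approximately 48 to 57 hours smoking abstinence and 1 day of single product use" per period. There is no Day 0. Section 10.5.2.1 states: "The start of the first product use must be in the window of 6:00 AM to 9:00 AM".

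- 23:00 on Day -3 to 06:00-09:00 on Day 1: 1 + 24 + 24 + 6 = 55 h, up to 58 h.
- Day 1 use to Day 3 use: 48 h, give or take the permitted 1 h.

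Both agree with the stated range, given that it is approximate. Counting from 23:00 on Day -3 is therefore how the plan itself reckons abstinence.

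**2. Place the CO tests on that clock.** Hours since 23:00 on Day -3:

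| Test | Clock time | Hours |
|---|---|---|
| Day -2, first | 08:00-09:30 | 9 to 10.5 |
| Day -2, second | 12:00-13:30 | 13 to 14.5 |
| Day -2, third | 16:00-17:30 | 17 to 18.5 |
| Day -2, fourth | 20:00-21:30 | 21 to 22.5 |
| Day -1, first | 08:00-09:30 | 33 to 34.5 |

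These are the shortest intervals. Anyone who stopped before 23:00 has longer.

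**3. CO at 23:00 that still leaves 10 ppm at the test.** With first-order decline, CO at time t is CO at 23:00 × 2^(−t/half-life). The level needed at 23:00 is therefore 10 × 2^(t/half-life). The SAP gives neither a half-life nor CO levels at 23:00. Half-lives of 4, 6 and 8 h are assumptions, shown as a range.

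Example: first Day -2 test, t = 9 h, half-life 6 h: 10 × 2^(9/6) = 28.3 ppm. At t = 10.5 h: 10 × 2^(10.5/6) = 33.6 ppm.

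| Test | 4 h | 6 h | 8 h |
|---|---|---|---|
| Day -2, first | 47.6-61.7 | 28.3-33.6 | 21.8-24.8 |
| Day -2, second | 95.1-123.4 | 44.9-53.4 | 30.8-35.1 |
| Day -2, third | 190.3-246.8 | 71.3-84.8 | 43.6-49.7 |
| Day -2, fourth | 380.5-493.5 | 113.1-134.5 | 61.7-70.3 |
| Day -1, first | 3044-3948 | 452.5-538.2 | 174.5-198.7 |

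(ppm at 23:00 above which a compliant subject is flagged)

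**4. Read in the other direction.** An assumed 40 ppm at 23:00 leaves, after 9 h, 8.4 ppm (4 h), 14.1 ppm (6 h) or 18.3 ppm (8 h). An assumed 20 ppm stays below 10 ppm for any half-life under 9 h. Whether a compliant subject is flagged at the first test thus depends on two quantities the SAP does not give. From Day -1 onward, residual CO from permitted smoking is not a plausible cause of a flag at any of these half-lives.

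**The case against.** The strongest reply is that little follows from the label.

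- **Exclusion is not automatic.** The major deviation in Table 9 is use of a product, not a CO reading. CO is one of several compliance measures under Section 6.3.3. A reviewer who sees a Day -2 morning value above 10 ppm falling through the day can recognise residual CO. This stands. A reader might infer that compliant heavy smokers will be lost from the PK population and the primary ratio biased. The SAP does not support that, given the review and the evaluability condition in Section 10.3.
- **Day -3 is a shortened smoking day.** Section 6.1 asks subjects not to smoke that morning and holds smoking back until two assessments are done. CO at 23:00 may therefore be below the habitual level. This stands and lowers the likely frequency. A reader might also infer that Day -2 non-compliance will be over-reported. Only the possibility is shown, because neither half-life nor CO at 23:00 is given.
- **The reporting isolates the issue.** Non-compliance is tabulated by study day, and CO values are listed with their times. Randomization is on Day -1, so residual CO on Day -2 cannot be an effect of sequence. This is true, but a cluster on Day -2 would not show whether it came from permitted or forbidden smoking. The table would still call those subjects non-compliant.

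The reply does not remove the mismatch itself: the rule covers the first Day -2 test, and nothing in the SAP allows for smoking permitted the night before.

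**Conclusion.** As written, Section 11.4 can label permitted smoking as non-compliance at the first Day -2 test. The 9 to 10.5 h interval follows directly from the SAP. The size of the risk rests on the assumed half-life and on first-order decline: a subject who smoked up to 23:00 is flagged if CO then exceeded about 48-62 ppm (4 h), 28-34 ppm (6 h) or 22-25 ppm (8 h). How many of the 48 subjects this would affect cannot be computed.

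The effect is confined to the Day -2 count in Table 15.2.5.1 and to false candidates for the Table 9 wash-out deviation. No effect on the primary Cmax or AUC(0-last) ratio is shown. This is a modest correction, worth making because it is cheap and because the compliance table is otherwise ambiguous on that day.

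**What to change.** Replace the rule in Section 11.4 with one sentence to this effect: exhaled CO above 10 ppm counts as non-compliance at the third and fourth tests on Day -2, at any test on Day -1 or Day 2, and before T0 on Day 1 and Day 3; the first two Day -2 values are reported descriptively only. Table 9 takes up the change through its reference to Section 11.4.

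The third test is at least 17 h after 23:00. A false flag there needs about 190, 71 or 44 ppm at 23:00 for half-lives of 4, 6 or 8 h. Starting only on Day -1 would be safer still against false flags, but would give up the late Day -2 tests, where such flags are already unlikely. Flagging a rise between consecutive Day -2 tests is not a good substitute: it would need a minimum size of rise, and the first test would have no suitable reference value.

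The cost is one sentence, with no change to data collection, models or sample size. The small downside is that covert smoking early on Day -2 whose CO has fallen to 10 ppm or below by 16:00 would not be flagged by this rule.

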11.5 Extent of Exposure (Product Consumption)

Details of the product test prior to enrollment and of product use after randomization will be listed by sequence for the Safety population.

The number and percentage of subjects who smoked 1, 2, 3, 4 or 5 CHTP 1.1 M sticks at admission will be tabulated.

The number and percentage of subjects who smoked 0 or 1 (category >1 will be included if applicable) CHTP 1.1 M sticks, or mCC during single use days (Day 1 or Day 3) will be tabulated by sequence.

The data will be presented in the below outputs:

TFL number	Title
TABLES	
15.2.2.1	Descriptive Statistics of Product Use - Safety Population
LISTINGS	
15.3.2.1	Listing of Product Usage

11.6 Planned Statistical Analyses

11.6.1 Primary Analyses

The primary parameters C_{\max} and $AUC_{(0-\text{last})}$ will be listed and summarized as described in Section 11.1 “General Considerations” and subsections. In addition plots of the data versus product will be provided.

The primary analysis of C_{\max} and $AUC_{(0-\text{last})}$ will be performed on the natural log-transformed parameters using an analysis of variance (ANOVA) model with terms for sequence, subject nested within sequence, period and product as fixed effect factors (Senn, 2002, FDA, 2001, CHMP, 2010 and CHMP Appendix IV, 2011).

Carry-over effect will not be tested, as it cannot be statistically distinguished from the interaction between product and period in a 2x2 crossover design.

The SAS code to be used is shown below:

```
Proc glm data=_data_ ;  
Class subject sequence product period ;  
Model log_pk = sequence subject(sequence) period product ;  
Lsmean product / pdiff =control('mCC') alpha=0.05 cl ;  
Test h=sequence e=subject(sequence) ;  
Run ;
```

where “log_pk” is the the natural log-transformed PK parameter being analyzed.

Supportive analysis will be performed as described in Section 11.6.3 "Supportive/Sensitivity Analysis".

LS means for each product will be back-transformed by exponentiation and will be tabulated together with the ratio (CHTP 1.1 M : mCC) and 95% CI.

The geometric CV will also be presented as $CV(\%) = 100\sqrt{(e^{\text{MSE}} - 1)}$, where MSE is the mean square error of the fitted model residual.

Exploratory subgroup analyses will be conducted for the primary endpoints in the following planned subgroups: sex (male or female), mCC nicotine level at Admission (ISO nicotine level ≤ 0.6 mg and >0.6 to ≤ 1 mg) provided there are more than 4 subjects in each category.

In case of any nicotine levels at T_0 greater than 5% of their C_{\max} value being observed, a supportive analysis as described in Section 11.6.3 "Supportive/Sensitivity Analysis" of the primary endpoints will be performed as described above, where the data of these subjects with nicotine levels at T_0 greater than 5% of their C_{\max} value will be excluded from the analysis.

Supportive analysis will be performed as described in Section 11.6.3 "Supportive/Sensitivity Analysis" in order to evaluate the sensitivity of CHTP 1.1 M effect estimates to methods used for missing data by means of a mixed model approach, should there be 20% or more missing parameter PK values.

The data will be presented in the below outputs:

TFL number	Title
TABLES	
15.2.3.1	Analysis of Primary Pharmacokinetic Parameters of Nicotine – PK Population
15.2.3.2.1	Analysis of Primary Pharmacokinetic Parameters of Nicotine by Sex– PK Population
15.2.3.2.2	Analysis of Primary Pharmacokinetic Parameters of Nicotine by Nicotine Level – PK Population
15.2.4.4	Descriptive Statistics of Pharmacokinetic Parameters of Nicotine – PK Population
15.2.4.4.1	Descriptive Statistics of Pharmacokinetic Parameters of Nicotine by Sex – PK Population
15.2.4.4.2	Descriptive Statistics of Pharmacokinetic Parameters of Nicotine by Nicotine Level – PK Population
FIGURES	
15.1.1.1	Primary Pharmacokinetic Parameters of Nicotine vs. product – PK Population
LISTINGS	
15.3.3.1	Listing of Pharmacokinetic Parameters of Nicotine
15.3.2.2	Individual Efficacy Response Data

